### 8.1.2 Information to be collected on screening failures

Participants who sign an informed consent form and subsequently found to be ineligible will be considered a screen failure. The reason for screen failure should be entered on the applicable Case Report Form. The demographic information, informed consent, and Inclusion/Exclusion pages must also be completed for screen failure participants. No other data will be entered into the clinical database for participants who are screen failures, unless the participant experienced a serious adverse event during the screening period (see [Section 10.1.6](#) for reporting details).

Participants who sign an informed consent and are considered eligible but fail to be started on treatment for any reason will be considered an early terminator. The reason for early termination should be captured on the appropriate disposition Case Report Form.

## 8.2 Participant demographics/other baseline characteristics

Country-specific regulations should be considered for the collection of demographic and baseline characteristics in alignment with CRF.

The data that will be collected on patient characteristics at screening include:

- Demography (age, sex, race, ethnicity), if local regulations allow for the collection of such information
- Diagnosis and extent of cancer: patient's cancer history, including documented primary location of cancer, date of diagnosis, presence of metastases with specification of the metastatic site(s) and tumor grading at study entry.

- Somatostatin receptor imaging (SRI) data obtained within 3 months prior to screening visit date will be collected to confirm the diagnosis and somatostatin uptake.
- A CT/MRI assessment will be performed during the screening period to assess the status of the disease.
- Prior antineoplastic medications/radiotherapy/surgery: information pertaining to any chemotherapy, hormonal therapy, immunotherapy, radiation, or surgery the patient has previously received.
- Other medical history (e.g. important medical, surgical, and allergic conditions from the subject's medical history which could have an impact on the subject's evaluation) / current medical conditions (e.g., all relevant current medical conditions which are present at the time of signing informed consent).
- Data from the following baseline assessments:
  - Physical examination (only abnormalities resulting from physical exam will be recorded in eCRF)
  - Vital signs
  - ECG
  - Height and weight measurement
  - Laboratory assessments (biochemistry, hematology, urinalysis, safety biomarkers for endocrine and gonadal function, growth and bone development)

### **8.3 Dosimetry**

Patients will have whole body and organ radiation dosimetry (including the critical organs, i.e. bone marrow and kidney) determined following the first Lutathera treatment using planar imaging and blood radioactivity data. In the exceptional circumstances when dosimetry cannot be done in a particular patient after the first dose, it should be done as soon as feasible upon a later dose. For each patient, dosimetry will be performed only once throughout the study.

Dosimetry assessments will be performed as follows:

- Whole body planar image will be acquired on Day 1 (1 to 3 hours after end of Lutathera infusion), 2, 3, 4 and 8 of Week 1
- SPECT/CT scan will be acquired in 24 hours after the end of Lutathera infusion (on Day 2)
- Blood samples for radioactivity measurement will be collected before the start of Lutathera infusion, at the end of Lutathera infusion, then at 2h, 6h, 24h and 72h after the end of Lutathera infusion
- All excreted urine from the start of Lutathera infusion until the first whole body planar imaging will be collected, its volume measured and the radioactivity concentration (kBq/mL) determined in order to calculate the total radioactivity excreted from the body from the start of Lutathera infusion to the time of the first scan. Patients should be asked to void before starting the infusion, so that the chances of voiding after the start of Lutathera before the first whole body planar imaging are minimized. If no urine is excreted from the start of Lutathera infusion until the first whole body planar imaging, no urine dosimetry is necessary.

### **8.3.1 Whole body planar and SPECT/CT Images**

Whole body planar and SPECT/CT images will be obtained at the investigational sites and then provided to a selected vendor for evaluation as DICOM files, which will be made available through a web-exchange system or other suitable IT support (e.g. compact disks). For more details about the images transfer and analysis refer to the dosimetry manual provided to the sites.

### **8.3.2 Methods used to estimate absorbed radiation doses**

According to the Medical Internal Radiation Dose scheme ([Bolch 2009](#), [Loevinger 1988](#), [ICRU 1979](#), [NCRP 1985](#)), the radiation dose to a target organ is the sum of the self-dose from this organ and the cross doses from all other target organs. In order to calculate the radiation dose to the various target organs the amount of radioactivity present in the source organs must be measured. The radioactivity uptake in each organ is determined at various time points. This uptake defines the kinetics of the radiopharmaceutical. By integrating such time-activity curve, the number of decays from each source organ per injected activity dose is obtained, and this is the so-called time Integrated Activity Coefficient (TIAC). The TIACs from each organ will be processed by Olinda/EXM software for the calculation of the organ absorbed radiation doses.

### **8.3.3 Biological samples for PK and dosimetry analysis**

Radioactivity in blood and urine will be measured at the investigational sites with a properly calibrated gamma counting system.

The results of the activity concentration in the blood and urine samples (if measured locally) and the volume of the urine excreted before the first scan will be used for PK and dosimetry calculations.

#### **a. Blood sample counting**

Whole blood samples (1 mL in heparinized tubes) will be collected from each patient at pre-defined time points and counted in a properly calibrated gamma-counter.

The acquired blood radioactivity data will be used for both dosimetry and PK assessments.

#### **b. Urine sample counting**

The majority of the infused Lutathera is excreted via the kidneys into the urine.

The total radioactivity excreted in urine before the first image acquisition will be determined, as this information is needed for dosimetry evaluation. The total cumulative volume of urine eliminated in that interval (from the administration to the first whole body planar imaging) will be measured. A urine sample (1 mL) will be taken from the total volume eliminated in that period for radioactivity measurement by gamma-counter. If no urine is excreted from the start of Lutathera infusion until the first whole body planar imaging, no urine dosimetry is necessary.

### 8.3.4 Dosimetry equipment and timepoints

The following equipment is necessary for the data acquisition:

1. A gamma-camera with medium energy collimator.
2. Well counter with multichannel analyser or gamma counter to determine  $^{177}\text{Lu}$  radioactivity in blood and urine samples.
3. A dose calibrator (activimeter) to measure the radioactivity in the reference source and the injected radioactivity.
4. SPECT/CT equipment

A detailed schedule of the dosimetry assessments is shown in the [Table 8-3](#) below.

**Table 8-3 Dosimetry assessments timepoints**

|                                      | Cycle 1 / Week 1                          |  |    |                       |                 |    |              |               |               |               |                |  |  |
|--------------------------------------|---|--|----|-----------------------|-----------------|----|--------------|---------------|---------------|---------------|----------------|--|--|
|                                      | Day 1                                     |  |    |                       |                 |    | Day 2        | Day 3         | Day 4         | Day 8         |                |  |  |
| Lutathera administration             |   | X (30-min $\pm 10$ min infusion)   |    |                       |                 |    |              |               |               |               |                |  |  |
| Amino acid administration            | X
(4-h infusion (max 6 h))             |  |    |                       |                 |    |              |               |               |               |                |  |  |
| Hours from end of Lutathera infusion | Pre-dose                                  |  | 0h | 1h                    | 2h $\pm 30$ min | 3h | 6h $\pm 1$ h | 24h $\pm 4$ h | 48h $\pm 6$ h | 72h $\pm 6$ h | 168h $\pm 6$ h |  |  |
| Blood sampling for dosimetry         | X
(Any time before Lutathera infusion) |  | X  |                       | X               |    | X            | X             | X             |               |                |  |  |
| Whole body planar imaging            |   |  |    | X
(any time 1-3 h) |                 |    | X            | X             | X             | X             |                |  |  |
| Urine collection for dosimetry       |   | X
(from start of Lutathera infusion to 1 st whole body planar imaging) |    |                       |                 |    |              |               |               |               |                |  |  |
| SPECT/CT imaging                     |   |  |    |                       |                 |    | X            |               |               |               |                |  |  |

The intervals for dosimetry sampling and imaging in [Table 8-3](#) are recommended and acceptable variations. However, if an assessment cannot be done within specified windows, it can be done at the closest feasible time, even if outside of the window.

Blood sampling times for dosimetry and PK assessments have been optimized based on a population PK model developed in adults to provide robust estimates of individual patient pharmacokinetic parameter values.

### **8.3.5 Dosimetry and PK parameters**

Lutathera bio-distribution, dosimetry and absorbed dose in critical organs will be determined from Time activity Curves (TACs) derived from radioactivity measured in blood and urine samples and in Regions of interest (ROI) for organs and tumor lesions drawn using the acquired planar images. Dosimetry calculations will be performed from the analyses of organs having significant uptake, identified visually. ROI delimiting these organs are used to determine relative radiotracer uptake calculated as a percentage of the injected dose. TACs are derived from mono-, bi-, or tri-exponential functions with best fit to time course data. By integrating the TACs, the Time Integrated Activity Coefficients (TIACs) are obtained. TIACs, also called Number of Decays, will be used to calculate the absorbed radiation dose values (Gy) in target organs.

The absorbed radiation dose in organs is the ultimate output dosimetry parameter that will be provided to Investigators for each patient, and to DSMB, if necessary (see [Section 6.5.1.2](#)).

Pharmacokinetic parameters such as the maximum blood concentrations (Cmax), the sampling time at which Cmax is reached (tmax), in addition to the area under the curve (AUC0-∞), systemic clearance (Cl), volume of distribution (V1 and V2) will be determined using model based methods. Other parameter estimates may be determined as deemed appropriate.

## **8.4 Safety assessments**

### **8.4.1 Adverse Event Monitoring**

All adverse events (AEs), whether or not spontaneously reported by the patient, will be recorded starting from the signing of the ICF until the end of the Treatment Period. During the Follow-up Period only related serious adverse events (SAE) and adverse events of special interest (AESI) will be recorded, except for all secondary malignancies which need to be recorded as AESI irrespective of causality. For details on AE definitions, collection and reporting refer to [Section 10](#).

In the case where patient on-site study visits are limited due to COVID-19 pandemic, regular phone or virtual calls will occur for safety monitoring and discussion of the participant's health status until the participant can again visit the site.

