## 2 Objectives and endpoints

**Table 2-1 Objectives and related endpoints**

|                  | Objectives   | Endpoints   |
|------------------|---|--|
| Primary   | 

• Evaluate organ absorbed radiation doses from PRRT with Lutathera in adolescent patients with SSTR-positive GEP-NETs and PPGLs as a pooled cohort

• Evaluate safety and tolerability of Lutathera in adolescents with SSTR-positive GEP-NETs and PPGLs as a pooled cohort

  | 

• Target organ (e.g. kidney and bone marrow) absorbed radiation doses in adolescents with SSTR-positive GEP-NETs and PPGLs as a pooled cohort

• The incidence of adverse events (AEs) and laboratory toxicities after the 1st Lutathera administration in adolescents with SSTR-positive GEP-NETs and PPGLs as a pooled cohort

   |
| Secondary | 

• Evaluate cumulative safety of Lutathera in adolescents with SSTR-positive GEP-NETs and PPGLs as a pooled cohort

• Evaluate long-term safety of Lutathera in adolescents with SSTR-positive GEP-NETs and PPGLs as a pooled cohort

• Perform comparative assessment of dosimetry and pharmacokinetics (PK) between adolescent patients with GEP-NETs and PPGLs as a pooled cohort and adult patients using the extrapolation model developed for the clinical study

 | 

• The incidence of adverse events (AEs) and laboratory toxicities until 6 months after the last Lutathera dose (short-term follow-up) in adolescents with SSTR-positive GEP-NETs and PPGLs as a pooled cohort

• The incidence of adverse events (AEs) and laboratory abnormalities during the long-term follow-up of 5 years after the last Lutathera dose in adolescents with SSTR-positive GEP-NETs and PPGLs as a pooled cohort

• Calculated organ absorbed doses and PK parameters based on imaging/blood radioactivity concentration data from adolescent with SSTR-positive GEP-NETs and PPGLs as a pooled cohort patients compared to the predicted distribution / organ absorbed doses

 |

|  |  |  |
|--|--|--|
|  |  |  |
|--|--|--|

---

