Therefore, to enable a follow-up on long-term safety risks in adolescent patients treated with Lutathera, a follow-up period of 5 years is included in the study. During the long-term follow-up, patient visits will occur every 6 months to collect information on adverse events, secondary malignancies, further anticancer treatments, as well as to draw laboratory samples for chemistry, hematology and safety biomarkers of growth and development, reproductive and endocrine function as well as bone formation.

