2. The investigator is obligated to assess the relationship between any treatment used in the study (study treatment, AxMPs) and each occurrence of each AE. The investigator will use clinical judgment to determine the relationship. A reasonable possibility of a relationship conveys that there are facts, evidence, and/or arguments to suggest a causal relationship, rather than a relationship cannot be ruled out. Alternative causes, such as underlying disease(s), concomitant therapy, and other risk factors, as well as the temporal relationship of the event to study intervention administration, will be considered and investigated. For causality assessment, the investigator will also consult the IB and/or product information, for marketed products. The causality assessment is one of the criteria used when determining regulatory reporting requirements.
3. Its duration (start and end dates) or if the event is ongoing, an outcome of not recovered/not resolved must be reported.
4. Whether it constitutes a Serious Adverse Event (see [Section 10.1.2](#) for definition of SAE) and which seriousness criteria have been met.
5. Action taken regarding study treatment
  - Dose not changed
  - Dose reduced

- Drug interrupted/withdrawn

6. Treatment for adverse events. All adverse events must be treated appropriately.

7. Its outcome i.e., its recovery status or whether it was fatal

If the event worsens, it should be reported a second time in the eCRF noting the start date when the event worsens in toxicity. For grade 3 and 4 adverse events only, if improvement to a lower grade is determined a new entry for this event should be reported in the eCRF noting the start date when the event improved from having been Grade 3 or Grade 4.

Once an adverse event is detected, it must be followed until its resolution (or until it is judged to be permanent) or until 30 days after end of study visit. Assessments must be made at each visit (or more frequently, if necessary) of any changes in severity, the suspected relationship to the interventions required to treat it, and the outcome.

For the investigational product and for non-authorized AxMPs (when applicable), information about adverse drug reactions and how to manage them can be found in the Investigator's Brochure (IB) or equivalent documentation. Information about adverse drug reactions can also be found in the product information for marketed products.

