#### **10.1.5 Adverse Events of Special Interest**

Adverse events of special interest (AESI) are defined as events (serious or non-serious) which are ones of scientific and medical concern specific to the Sponsor’s product or program, for which ongoing monitoring and rapid communication by the Investigator to the Sponsor may be appropriate. Such events may require further investigation in order to characterize and understand them.

These potential risks deserve special attention even if they do not fulfill any of the seriousness criteria. These non-serious adverse events of special interest (AESI) should be reported to the Sponsor using reporting procedures for SAEs. During screening, only AESI meeting seriousness criteria should be reported to the Sponsor. During the treatment period, all AESI need to be reported to the Sponsor irrespective of causality. During the follow-up period, AESI need to be reported only if considered related to the study treatment except for all secondary malignancies which need to be reported as AESI irrespective of causality. The AESI represent main risks of Lutathera and amino acid treatment reported in adults, as well as potential risks in pediatric population ([Table 10-1](#)).

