**Nephrotoxicity:** Since Lutathera is cleared through the kidneys and reabsorbed by the kidneys, the kidneys have always been considered the “critical organs”. An infusion of amino acid is used for kidneys protection by inhibition of tubular reabsorption of Lutathera. Pursuant to these risk minimization efforts and in addition to the criteria of dose-modifying toxicities and criteria of inclusion (at baseline and before subsequent treatments) pertinent to renal function measurements, renal and urinary tract toxicities are considered AESI. Investigators must report as AESI renal toxicities including renal failure (ranging from significantly reduced measured or estimated creatinine clearance to clinically overt renal failure other than that of obvious non-IMP-induced origin), suspected radiation nephropathy of any type, such as radiation-induced thrombotic microangiopathy (manifested with, e.g., proteinuria, hypertension, edema, anaemia, decrease serum haptoglobin), or general symptoms and signs of acute radiation toxicity (e.g., increased frequency and urgency of urination, nocturia, dysuria, bladder spasm, bladder obstruction, genitourinary ulceration or necrosis).

**Endocrine (hypothalamic-pituitary and growth) disorders:** Since the potential effect of the Lutathera treatment on the pituitary-gonadal and pituitary-thyroid axes is not well described in the adolescent population, the endocrine effects will be closely monitored via specific biomarkers. Any suspected endocrine toxicity should be considered AESI regardless of severity.

**Effects on bone development:** Radiation exposure has a potential effect on the overall quantity and quality of bone by interfering with the trabecular architecture through increased osteoclast activity and decreased osteoblast activity. Biomarkers of bone metabolism help to detect the metabolic imbalance and identify bone toxicities. Any suspected bone toxicity should be considered AESI regardless of severity.

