**Table 10-2 Reporting rules and timeframe**

| Event           | During Screening                                     | During Treatment period  | During Follow-up period   | Reporting timeframe          |
|-----------------|--|--|---|------------------------------|
| Non-serious AEs | Not reported   | Not reported   | Not reported  | Not applicable               |
| SAEs            | Only SAEs potentially related to any study procedure | All SAEs, regardless of causality, until 8 weeks + 30 days after last dose | SAEs to be reported only if the investigator suspects a causal relationship to study treatment  | Within 24 hours of awareness |
| AESI            | Only if SAE, see above                               | All AESI irrespective of causality   | AESI to be reported only if considered related to the study treatment except for all secondary malignancies which need to be reported as AESI irrespective of causality | Within 24 hours of awareness |
| Pregnancy       | To be reported                                       | To be reported   | To be reported  | within 24 hours of awareness |

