#### **2.6.1.1 Adverse events of special interest / grouping of AEs**

During the treatment period, all AESIs are to be reported to the Sponsor irrespective of causality. During the follow-up period, AESIs are to be reported only if considered related to the study treatment except for all secondary malignancies which need to be reported as AESIs irrespective of causality. The AESIs represent main risks of Lutathera and amino acid treatment reported in adults, as well as potential risks in pediatric population.

The selection of the AESIs will be initially based on the classification of the AEs as reported in the Adverse Event eCRF page.

Additional groupings of AESIs above and beyond those flagged in the eCRF may also be examined in this study. These groupings are defined using MedDRA terms, SMQs (standardized MedDRA queries), HGLTs (high level group terms), HLT (high level terms) or PTs. Customized SMQs (Novartis MedDRA queries, NMQ) may also be used. A NMQ is a customized group of search terms which defines a medical concept for which there is no official SMQ available or the available SMQ does not completely fit the need. It may include a combination of single terms and/or an existing SMQ, narrow or broad.

The grouping of AEs in AESI according to project standards will be specified in the electronic Case Retrieval Strategy (eCRS) or separate listing in case of the AESI category is not included in the eCRS, and may be regularly updated.

All AESI categories will be summarized for those events occurring on-treatment. Events starting during the short-term and long-term follow-up periods will be listed.

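### From day 57 after the last dose, clinical adverse events are recorded only if judged related, so the AE part of the 6-month and 5-year safety endpoints cannot be estimated as worded

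*Protocol*

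**What the plan says.** **Endpoints.** Protocol Table 2-1 and SAP Table 1 define the cumulative-safety endpoint as AE incidence and laboratory toxicities up to 6 months after the last dose. The long-term endpoint is AE incidence and "laboratory abnormalities during the long-term follow-up of 5 years after the last Lutathera dose". Neither mentions relatedness.

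**Collection.** All AEs are recorded from consent to the end of the treatment period. After that, Protocol 8.4.1 says: "During the Follow-up Period only related serious adverse events (SAE) and adverse events of special interest (AESI) will be recorded", and then exempts secondary malignancies. Read alone, that sentence leaves open whether relatedness also governs adverse events of special interest (AESIs). Section 10.1.5 settles it: "During the follow-up period, AESI need to be reported only if considered related to the study treatment except for all secondary malignancies". Section 10.1.6, Table 10-2 ("AESI to be reported only if considered related to the study treatment except for all secondary malignancies") and SAP 2.6.1.1 ("During the follow-up period, AESIs are to be reported only if considered related to the study treatment") agree. The AESIs affected are haematological, renal, endocrine, bone, and cardiovascular or electrolyte events.

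**Who decides.** Section 10.1.1: "The investigator will use clinical judgment to determine the relationship". The study is single-arm and open-label (Section 6.4).

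**SAEs.** Section 10.1.6 and Table 10-2 keep SAE reporting all-cause until 30 days after the end-of-treatment (EoT) visit.

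**Analysis.** SAP 2.6.1 and 2.6.1.1 summarise on-treatment AEs and AESIs. Events that start in follow-up are listed only.

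**The concern.** An endpoint that counts adverse events needs those events to be collected. In follow-up, an AESI judged unrelated is not recorded, and non-serious events outside the AESI categories are not recorded whether related or not. Relatedness therefore acts as a condition for entering the database, when it should be an attribute recorded for each event.

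The filter works in one direction, because it can only remove events. It is least secure for endocrine events. Section 10.1.5 says the potential effect on the pituitary-gonadal and pituitary-thyroid axes "is not well described in the adolescent population, the endocrine effects will be closely monitored via specific biomarkers". Section 10.1.1 asks for positive grounds for a causal link and does not accept mere inability to rule one out. An uncertain endocrine event can fail that test and leave no AE record.

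Renal events have a similar problem. Section 4.3 describes late renal failure in adults 3 to 36 months after treatment, in patients with underlying impairment or risk factors. The Amendment 02 rationale says patients with a history of nephrectomy are treated in this study. Competing explanations are therefore to be expected for the very events of interest.

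**Working it through.** **1. The plan's own detection figure.** Protocol Table 12-1 gives the chance of seeing at least one affected patient among 8 as 1 − (1 − p)^8. For p = 10, 20, 30, 40 and 50% this gives 57.0, 83.2, 94.2, 98.3 and 99.6%, so every cell is reproduced. The table concerns acute toxicity with every event recorded. It serves here only as a template.

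**2. Collection instructions side by side.**

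| Place | Follow-up instruction |
|---|---|
| Protocol 8.4.1 | Related SAEs and AESIs only; all secondary malignancies |
| Protocol 10.1.6, Table 10-2 | SAEs all-cause to 30 days after EoT, then related only |
| Protocol 4.3 | "During the long-term follow-up, patient visits will occur every 6 months to collect information on adverse events" |
| Protocol 8.4.2, 8.4.3, 8.4.6, 10.1.1 | Record AEs or relevant changes after consent or baseline; no period or causality limit |
| Protocol 9.1.1 | AEs and SAEs at abbreviated visits after stopping treatment; no causality limit |
| SAP 2.1.1 | Listings of related SAEs and AESIs |
| SAP 2.6.1 | All AEs and SAEs that start in follow-up listed |

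Two sites following different sections would record different events.

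**3. Data that escape the filter.** I take follow-up sampling from Section 4.3 and SAP 2.6.4. Chemistry, haematology and the endocrine, reproductive, growth and bone biomarkers are drawn every 6 months in long-term follow-up. Height is measured on the same cycle (Section 8.4.4). SAP 2.6.4 repeats the worst-grade and shift tables with follow-up data. SAP 5.3 grades laboratory values by program, without clinical assessment. SAP 2.6.5.2 summarises vital signs, including height, cumulatively over follow-up. None of this depends on causality.

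**4. Span of the filter.** For patients who complete treatment, the on-treatment period ends 56 days after the last dose (Protocol 12.5.2, SAP 2.1.1). Short-term follow-up runs from day 57 to day 183. Using the SAP month, 60 × 30.4375 = 1,826.25 days.

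- AESIs: (183 − 56)/183 = 127/183 = 69% of the 6 months; 1 − 56/1,826.25 = 97% of the 5 years.
- SAEs: the filter starts after day 56 + 30 = 86, so (183 − 86)/183 = 53% and 1 − 86/1,826.25 = 95%.

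**5. Possible loss, clinical component only.** Let p be the true proportion of patients with a given late clinical AESI and q the share of those events judged related. The documents give neither for late events, so both are assumptions. I take p from columns of Table 12-1 and vary q. P(at least one patient recorded) = 1 − (1 − pq)^n, with n = 8 (the planned minimum) or n = 11 (enrolled at Amendment 03).

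| n, p | q = 1 | 0.75 | 0.5 | 0.25 |
|---|---|---|---|---|
| 8, 30% | 94.2% | 87.0% | 72.8% | 46.4% |
| 8, 10% | 57.0% | 46.4% | 33.7% | 18.3% |
| 11, 30% | 98.0% | 93.9% | 83.3% | 57.6% |
| 11, 10% | 68.6% | 57.6% | 43.1% | 24.3% |

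Example: n = 8, p = 30%, q = 0.5 gives 1 − 0.85^8 = 72.8%.

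**The case against.** The strongest reply is that the safety signals that matter most are measured directly in every patient. A reader might infer that all renal, haematological, endocrine and bone safety over 5 years passes through the investigator's judgement, and that a late creatinine rise, cytopenia or growth failure never reaches the database. The documents do not support that. Step 3 shows that such changes are collected and tabulated regardless of causality, and Amendment 03 added endocrine and gonadal biomarkers to the long-term visits for this purpose. This part of the objection stands in full.

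Three further arguments stand in part:

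- **The 6-month endpoint is cumulative.** Counted from the first dose at 8-week intervals, all-cause AE recording covers 3 × 56 + 56 = 224 of 168 + 183 = 351 days, or 64%. The 69% figure describes only the time after the last dose.
- **Attribution is partly built into the AESI definitions.** Endocrine and bone AESIs are suspected toxicities, and nephrotoxicity excludes renal failure of obvious other origin. All-cause recording would not remove all judgement. However, the protocol already applies an irrespective-of-causality rule to these same definitions during treatment.
- **All-cause late events add noise.** In an uncontrolled cohort with advanced disease and no restriction on concomitant medication in follow-up (Section 6.2.2), this is true. A causality field with a related subset deals with most of it.

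Scheduled assays do not replace clinical events. Section 10.1.5 defines many AESIs by clinical findings or consequences: infection with cytopenia, haemorrhage, suspected radiation nephropathy, urinary symptoms, arrhythmia. Diagnoses, consequences and events between visits depend on AE recording.

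**Conclusion.** The point holds for the clinical AE/AESI component of both follow-up endpoints and not for the laboratory, biomarker or height data. As worded, the AE component cannot be estimated under the collection rule in Protocol 8.4.1. That conclusion rests on the text alone and needs no assumed rate. The AESI filter applies to about 69% of the 6 months and 97% of the 5 years after the last dose.

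The number of events lost is unknown. Step 5 gives a range that assumes a true rate, a share judged related, and no other route of detection, so it says nothing about laboratory-detectable changes. A single loss figure should not be read from it. The lack of blinding is unavoidable in a single-arm study and is not itself the fault. The fault is that relatedness decides whether a clinical event is recorded at all. The mismatch is worth correcting because the events concerned may not be recoverable at analysis.

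**What to change.** In Protocol 8.4.1, record all AESI categories on the AE eCRF to the end of the 5-year follow-up irrespective of causality, as is already done for secondary malignancies. Keep causality as a data field and show related events as a subset. The 24-hour sponsor reporting rules in Section 10.1.6 and Table 10-2 can stay as they are, so expedited reporting is not extended to unrelated events. The endpoint wording should then name the event classes actually collected.

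If this is not done, restate the AE component of both follow-up endpoints (Protocol Table 2-1, SAP Table 1) as related SAEs and AESIs plus all secondary malignancies, alongside all-cause laboratory abnormalities.

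In either case, reconcile Protocol 8.4.1 with 8.4.2, 8.4.3, 8.4.6, 9.1.1, 10.1.1 and 10.1.6, and SAP 2.1.1 with SAP 2.6.1.

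The cost is amendment wording, some extra AE records at visits already scheduled for about 11 patients, and some clearly unrelated events in the listings.
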